10.2.6 Autologous Stem Cell Transplantation

In patients who elect to undergo stem cell harvesting, high dose chemotherapy, and autologous peripheral blood stem cell transplantation, CD34+ yield and time to neutrophil and platelet engraftment (counted from the day of stem cell infusion = day 0) will be reported.

10.2.7 Pharmacodynamics

See under correlative science (5.5).

10.3 Statistical Methodology

The Kaplan-Meier method will be used to report progression free survival and overall survival for patients treated at the HTLD / HTLD-CKD and for the entire study cohort but excluding patients who elect to undergo high dose chemotherapy and autologous stem cell transplantation. For statistical methods pertaining to pharmacodynamic analyses please see under correlative science (5.5).

11 Regulatory Considerations

11.1 Institutional Review Board/Ethics Committee Approval

The protocol for this study has been designed in accordance with the general ethical principles outlined in the Declaration of Helsinki. The review of this protocol by the IRB/EC and the performance of all aspects of the study, including the methods used for obtaining informed consent, must also be in accordance with principles enunciated in the declaration, as well as ICH Guidelines, Title 21 of the Code of Federal Regulations (CFR), Part 50 Protection of Human Subjects and Part 56 Institutional Review Boards.

The Investigator will be responsible for preparing documents for submission to the relevant IRB/EC and obtaining written approval for this study. The approval will be obtained prior to the initiation of the study.

The approval for both the protocol and informed consent must specify the date of approval, protocol number and version, or amendment number.

Any amendments to the protocol after receipt of IRB/EC approval must be submitted by the Investigator to the IRB/EC for approval. The Investigator is also responsible for notifying the IRB/EC of any serious deviations from the protocol, or anything else that may involve added risk to subjects.

Any advertisements used to recruit subjects for the study must be reviewed and approved by the IRB/EC prior to use.

11.2 Informed Consent

The Investigator must obtain informed consent of a subject or his/her designee prior to any study related procedures as per GCPs as set forth in the CFR and ICH guidelines.

Documentation that informed consent occurred prior to the subject's entry into the study and the informed consent process should be recorded in the subject's source documents. The original consent form signed and dated by the subject and by the person consenting the subject prior to the subject's entry into the study, must be maintained in the Investigator's study files.

11.3 Subject Confidentiality

Celgene affirms the subject's right to protection against invasion of privacy. In compliance with United States federal regulations, Celgene requires the Investigator to permit representatives of Celgene Corporation and, when necessary, representatives of the FDA or other regulatory authorities to review and/or copy any medical records relevant to the study in accordance with local laws.

Should direct access to medical records require a waiver or authorization separate from the subject's statement of informed consent, it is the responsibility of the Investigator to obtain such permission in writing from the appropriate individual.

11.4 Study Records Requirements

The Investigator must ensure that the records and documents pertaining to the conduct of the study and the distribution of the protocol therapy, that is copies of CRFs and source documents (original documents, data, and records [e.g., hospital records; clinical and office charts; laboratory notes; memoranda; subject's diaries or evaluation checklists; SAE reports, pharmacy dispensing records; recorded data from automated instruments; copies or transcriptions certified after verification as being accurate copies; microfiches; photographic negatives, microfilm, or magnetic media; x-rays; subject files; and records kept at the pharmacy, at the laboratories, and at medico-technical departments involved in the clinical study; documents regarding subject treatment and drug accountability; original signed informed consents, etc.]) be retained by the Investigator for as long as needed to comply with national and international regulations (generally 2 years after discontinuing clinical development or after the last marketing approval). The Investigator agrees to adhere to the document/records retention procedures by signing the protocol.

Females of childbearing potential (FCBP)[†] must agree to use two reliable forms of contraception simultaneously or to practice complete abstinence from heterosexual intercourse during the following time periods related to this study: 1) for at least 28 days before starting lenalidomide; 2) while participating in the study; and 3) for at least 28 days after discontinuation from the study. The two methods of reliable contraception must include one highly effective method (i.e. intrauterine device (IUD), hormonal [birth control pills, injections, or implants], tubal ligation, partner's vasectomy) and one additional effective (barrier) method (i.e. latex condom, diaphragm, cervical cap). FCBP must be referred to a qualified provider of contraceptive methods if needed.

Because of the increased risk of venous thromboembolism in patients with multiple myeloma taking lenalidomide and dexamethasone, combined oral contraceptive pills are not recommended with regimens combining lenalidomide and dexamethasone. If a patient is being treated with a regimen combining lenalidomide and dexamethasone and is currently using combined oral contraception, the patient should switch to one of the other highly effective contraceptive methods listed above. The risk of venous thromboembolism continues for 4–6 weeks after discontinuing combined oral contraception. The efficacy of contraceptive steroids may be reduced during co-treatment with dexamethasone.

Before starting lenalidomide:

Female Subjects:

- FCBP must have two negative pregnancy tests (sensitivity of at least 50 mIU/mL) prior to prescribing lenalidomide. The first pregnancy test must be performed within 10-14 days prior to prescribing lenalidomide and the second pregnancy test

[†] A female of childbearing potential is a sexually mature woman who: 1) has not undergone a hysterectomy or bilateral oophorectomy; or 2) has not been naturally postmenopausal for at least 24 consecutive months (i.e., has had menses at any time in the preceding 24 consecutive months).

must be performed within 24 hours prior to prescribing lenalidomide (prescriptions must be filled within 7 days). The subject may not receive lenalidomide until the Investigator has verified that the results of these pregnancy tests are negative.

Male Subjects:

- Must agree to use a latex condom during sexual contact with females of childbearing potential while participating in the study and for at least 28 days following discontinuation from the study even if he has undergone a successful vasectomy.

During study participation and for 28 days following discontinuation from the study:

All Subjects:

- If pregnancy or a positive pregnancy test does occur in a study subject or the partner of a male study subject during study participation, lenalidomide must be immediately discontinued.

Female Subjects:

- FCBP with regular or no menstrual cycles must agree to have pregnancy tests weekly for the first 28 days of study participation and then every 28 days while on study, at study discontinuation, and at day 28 following discontinuation from the study. If menstrual cycles are irregular, the pregnancy testing must occur weekly for the first 28 days and then every 14 days while on study, at study discontinuation, and at days 14 and 28 following discontinuation from the study.
- In addition to the required pregnancy testing, the Investigator must confirm with FCBP that she is continuing to use two reliable methods of birth control at each visit.
- Pregnancy testing and counseling must be performed if a subject misses her period or if her pregnancy test or her menstrual bleeding is abnormal. Lenalidomide treatment must be discontinued during this evaluation.

Male Subjects:

- Must agree to use a latex condom during sexual contact with females of childbearing potential while participating in the study and for at least 28 days following discontinuation from the study even if he has undergone a successful vasectomy.

Appendix II: ECOG Performance Status Scale

SCORE	DESCRIPTION
0	Fully active, able to carry on all pre-disease performance without restriction.
1	Restricted in physically strenuous activity but ambulatory and able to carry out work of a light or sedentary nature, e.g., light house work, office work.
2	Ambulatory and capable of all self-care but unable to carry out any work activities. Up and about more than 50% of waking hours.
3	Capable of only limited self-care, confined to bed or chair more than 50% of waking hours.
4	Completely disabled. Cannot carry on any self-care. Totally confined to bed or chair.
5	Dead.

Appendix III : NCI CTC Version 4.0

Toxicity will be scored using NCI CTC Version 4.0 for toxicity and adverse event reporting. A copy of the NCI CTC Version 4.0 can be downloaded from the CTEP homepage: (<http://ctep.info.nih.gov>). All appropriate treatment areas have access to a copy of the CTC Version

Appendix IV : Cockcroft-Gault estimation of CrCl

Cockcroft-Gault estimation of creatinine clearance (CrCl):
(Cockcroft, 1976; Luke 1990)

$$\text{CrCl (mL/min)} = \frac{(140 - \text{age}) \times (\text{weight, kg})}{72 \times (\text{serum creatinine, mg/dL})}$$

$$\text{CrCl (mL/min)} = \frac{(140 - \text{age}) \times (\text{weight, kg})}{72 \times (\text{serum creatinine, mg/dL})} \times 0.85$$

Appendix V: Bone marrow aspirations RV0507

Date:

Patient study number:

Aspiration sequence

1. Two 20mL heparin syringes, each pre-filled with 2mL of heparin
2. One 10mL heparin syringe pre-filled with 1mL heparin

Distribution

1. Page [name] for pick-up of the two 20mL syringes and this sheet
2. Send the 10mL syringe to pathology for cytogenetics and FISH (both Mayo send-out, sent by our pathology department)

Outside CCF:

Please either page or email [name] when sample is shipped:

Email: [contact]

Paging: [contact] – [name] followed by the # sign – enter call back number followed by # sign

Appendix VI: Blood draws for correlative science RV0507

Date:

Patient study number:

Obtain 10mL heparin (green top tube) and 10mL EDTA (two purple top tubes)

Page [name] for sample pickup

Outside CCF:

Please either page or email [name] when sample is shipped:

Email: [contact]

Paging: [contact] – [name] followed by the # sign – enter call back number followed by # sign

Appendix VII: Lenalidomide and dexamethasone drug administration diary

Cycle # :

Date of day 1 of above cycle:

Patient study number:

Revlimid® (lenalidomide) should be taken from day 1-21 and dexamethasone on day 1, 8, 15, and 22. On the table “R” represents Revlimid® and “D” represents dexamethasone.

Please call your study nurse when you take the 21st dose of Revlimid®, to allow time for the next order and ensure you have Revlimid® on time for the next cycle.

Please cross out the R if you took Revlimid® and cross out the D if you took dexamethasone on the indicated days. Please leave blank if you did not take the indicated drugs on the respective day, irrespective of the reason, whether you were advised by your physician or simply forgot.

Day 1 R	Day 2 RD	Day 3 R	Day 4 R	Day 5 R	Day 6 R	Day 7 R
Day 8 R	Day 9 RD	Day 10 R	Day 11 R	Day 12 R	Day 13 R	Day 14 R
Day 15 R	Day 16 RD	Day 17 R	Day 18 R	Day 19 R	Day 20 R	Day 21 R (call)
Day 22	Day 23 D	Day 24	Day 25	Day 26	Day 27	Day 28

Received by study nurse on:

(date as MM/DD/YY)

Name of study nurse:

Signature of study nurse:

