
twice a week, together with standard dose lenalidomide and low dose dexamethasone in relapsed or refractory myeloma patients in a phase I/II study with 10 additional patients enrolled at the highest tolerated low azacitidine dose to obtain an initial impression of efficacy and to evaluate whether this dose exerts the expected pharmacodynamic effects in myeloma cells before a larger phase II trial may be conducted. In light of new data supporting use of standard-dose azacitidine in myeloid neoplasia patients with kidney dysfunction(14) and GFR-adjusted lenalidomide for myeloma patients(15), amendment 7 extends the safety and preliminary efficacy evaluations to myeloma patients with GFR 30-59 ml/min (Cockroft-Gault). Lenalidomide will be used at a fixed dose of 10mg daily from day 1-21 every 28 days which yielded equal AUC concentrations in myeloma patients with GFR 30-49m/min as 25mg daily from day 1-21 every 28 days in patients with GFR \geq 80 ml/min in a recent study(15). Only two dose levels of azacitidine will be tested. Dose level "CKD 1" will use azacitidine at 40 mg/m² s.c. twice a week which has been found tolerable in patients with GFR \geq 60 ml/min; one of six patients developed a dose limiting toxicity, culture negative neutropenic fever at an absolute neutrophil count (ANC) nadir of 0.48K/mm³, with resolution the next day at an ANC of 0.89K/mm³ without G-CSF use. At the time of amendment 7, two patients with normal kidney function have completed the first cycle at dose level 5 (azacitidine 50mg/m² s.c. twice a week) without dose limiting toxicities. Six patients with GFR 30-59 ml/min will be treated at CKD 1 if dose limiting toxicities (DLTs) do not occur in more than one patient. If 2 of 3 or 2 of up to six patients develop DLTs at CKD1, subsequent patients will be treated at "CKD -1" (30mg/m² s.c. twice a week). Otherwise (no more than one patient with DLTs at CKD1), subsequent patients will receive azacitidine at 50mg/m² s.c. twice a week (= dose level CKD2). Lower or higher dose levels will not be tested. This modified dose escalation scheme increases safety by enrolling at least 6 patients per dose level and guarantees that the tolerability of twice a week azacitidine in patients with GFR 30-59 ml/min will be defined by enrolling maximally 12 additional patients. Omission of weekly azacitidine is based on the observation that clinical benefit response rates were more than twice as high with twice a week than with weekly azacitidine dosing (40% versus less than 15%) in patients with GFR > 60ml/min, an encouraging result taking into consideration that patients had received a median of 4.5 prior regimens, with myeloma refractory to previous lenalidomide in 88%, to previous proteasome inhibitors in 81%, and to both lenalidomide and proteasome inhibitors in 75%. Once the highest tolerated low dose for patients with reduced GFR (HTLD-CKD) has been defined, enrollment at this dose level may contribute to the 10 patient phase II extension. Before amendment 7 eighteen patients have started treatment, including two at dose level 5. Assuming up to 6 patients will be enrolled per dose level; the maximal number of enrolled patients will therefore increase from previously estimated 40 to 44 after amendment 7.

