5.6.2.3 Combination Therapy

Dosing Schedule for Patients with GFR \geq 60ml/min (Cockroft-Gault)

Dose level	Azacitidine (s.c.)* Starting day 1	Lenalidomide (p.o.) Starting day 1	Dexamethasone (p.o.)
------------	---------------------------------------	---------------------------------------	----------------------

1	30mg/m ² once a week ¹	25mg d1-21 every 28d ³	40mg p.o. once a week ⁴
2	40mg/m ² once a week ¹	25mg d1-21 every 28d ³	40mg p.o. once a week ⁴
3	30mg/m ² s.c. twice a week ²	25mg d1-21 every 28d ³	40mg p.o. once a week ⁴
4	40mg/m ² s.c. twice a week ²	25mg d1-21 every 28d ³	40mg p.o. once a week ⁴
5	50mg/m ² s.c. twice a week ²	25mg d1-21 every 28d ³	40mg p.o. once a week ⁴

* After highest tolerated low dose (HTLD) of azacitidine determination, azacitidine starting dose will be at the HTLD

Dosing Schedule for Patients with GFR 30-59ml/min (Cockcroft-Gault)

Dose level	Azacitidine (s.c.)* Starting day 1	Lenalidomide (p.o.) Starting day 1	Dexamethasone (p.o.)
-1	30mg/m ² s.c. twice a week ²	10mg d1-21 every 28d ³	40mg p.o. once a week ⁴
1	40mg/m ² s.c. twice a week ²	10mg d1-21 every 28d ³	40mg p.o. once a week ⁴
2	50mg/m ² s.c. twice a week ²	10mg d1-21 every 28d ³	40mg p.o. once a week ⁴

* After highest tolerated low dose (HTLD-CKD) of azacitidine determination, azacitidine starting dose will be at the HTLD-CKD

¹ Ideally, azacitidine is administered on the same day each week, but +/- up to two days is allowed, individual doses should be at least 5 days apart. Rotation of injection sites is obligatory.

² Azacitidine should be administered on the same days each week, +/- one day is allowed but there should be at least 48hrs between doses. The following schedules are recommended: Monday-Thursday, Monday-Friday, Tuesday-Friday, Tuesday-Saturday. Rotation of injection sites is obligatory

³: Lenalidomide dosing will be in the evening at approximately the same time each day. Prescriptions must be filled within 7 days. If a dose of lenalidomide is missed, it should be taken as soon as possible on the same day. If it is missed for the entire day, it should not be made up. Patients who take more than the prescribed dose of lenalidomide should be instructed to seek emergency medical care if needed and contact study staff immediately.

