⁴: Dexamethasone dosing, independent of age, will be in the morning with breakfast. Dexamethasone should be taken at least 24h after and not less than 24h before azacitidine to maximize the s-phase specific epigenetic effects of azacitidine.

5.6.2.4 Lenalidomide Maintenance Treatment and Guidelines for Re-Introduction of Azacitidine and Dexamethasone

After six 28-day cycles on combination therapy, dexamethasone and azacitidine will be discontinued and lenalidomide will be continued as a single agent at the last tolerated dose until disease progression. At physician discretion, for patients with response < PR after six 28-day cycles on combination therapy, the dose of lenalidomide may be

escalated during maintenance treatment to a maximum dose of 25mg daily on Days 1-21 of each 28-day cycle. Lenalidomide dose titration may only occur at the start of a new cycle of maintenance one dose level at a time, and only in patients who completed the previous treatment cycle without dose modifications or treatment delays due to toxicity. Lenalidomide dose titration may occur NOT more frequently than once every 28 days. After 12 months since initiation of protocol therapy, no further lenalidomide dose titration is permitted. Also for patients with response < PR after six 28-day cycles on combination therapy, dexamethasone and/or azacitidine may be continued or restarted (if it had been discontinued) at physician discretion. In particular, patients with response < PR after six 28-day cycles on combination therapy that have not shown sufficient signs of end organ improvement should be considered for lenalidomide dose titration and/or additional dexamethasone and/or azacitidine as outlined above. Similarly, patients who have achieved disease control (stable disease or better) during the first six 28-day cycles of combination therapy and who's myeloma progresses on maintenance therapy may be restarted on lenalidomide, azacitidine, and dexamethasone combination therapy at the last tolerated dose at physician discretion.

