5.7.1 Dose Modification Steps and Dose Re-Escalation Guidelines

5.7.1.1 Dose Modification Steps

Table 1: Lenalidomide dose modification steps for all toxicities listed in Table 5 EXCEPT for renal impairment or toxicities in the presence of renal impairment*

Current Lenalidomide Dose	One Level Dose Reduction
25 mg daily on Days 1-21 every 28 days	20 mg daily on Days 1-21 every 28 days
20 mg daily on Days 1-21 every 28 days	15 mg daily on Days 1-21 every 28 days
15 mg daily on Days 1-21 every 28 days	10 mg daily on Days 1-21 every 28 days
10 mg daily on Days 1-21 every 28 days	5 mg daily on Days 1-21 every 28 days
5 mg daily on Days 1-21 every 28 days	Discontinue lenalidomide

* Renal impairment is defined as calculated creatinine clearance \geq 30mL/min but $<$ 60mL/min (see Table 2 below for lenalidomide dosing)

Table 2: Lenalidomide dose modification steps for renal impairment (see Table 5) and for other toxicities which occur after dose reduction for renal impairment*

Current Lenalidomide Dose	One Level Dose Reduction
25 mg daily on Days 1-21 every 28 days	10 mg daily on Days 1-21 every 28 days
10 mg daily on Days 1-21 every 28 days	15 mg every 48 hours during Days 1-21 every 28 days
15 mg every 48 hours during Days 1-21 every 28 days	5 mg daily on Days 1-21 every 28 days
5 mg daily on Days 1-21 every 28 days	Discontinue lenalidomide

* Renal impairment is defined as calculated creatinine clearance $\geq 30\text{mL/min}$ but $< 60\text{mL/min}$

Table 3: Azacitidine Dose Adjustment Steps

Dose Level +2	100 mg/ m^2 SC twice a week (only for patients on twice a week azacitidine who tolerated azacitidine 75mg/ m^2 SC twice a week but did not respond, see under 5.7.1.2)
Dose Level +1	75 mg/ m^2 SC twice a week (only for patients on twice a week azacitidine who tolerated their full azacitidine starting dose but did not respond, see under 5.7.1.2)
Dose Level 0	Starting azacitidine dose (differs depending on cohort during phase I part, see 5.6.2.3)
Dose Level -1	Reduce dose by 50%, maintain frequency of administration
Dose Level -2	Discontinue azacitidine

Table 4: Dexamethasone Dose Reduction Step

Dose Level – 1	Reduce each dexamethasone dose by 50%
Dose Level – 2	Discontinue dexamethasone

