5.7.6 Treatment Compliance

Research center personnel will review the dosing instructions with subjects. Subjects will be asked to maintain a diary to record the drug administration (appendix VII). Subjects will be asked to bring any unused drug and empty drug containers to the research center at their next visit. Research personnel will count and record the number of used and unused drug at each visit and reconcile with the patient diary. Azacitidine will be administered at the Taussig Cancer Center and at University Hospital Ireland cancer Center, compliance will be assessed by review of medication administration reports. Any unused Revlimid® (lenalidomide) should be returned to the patient for disposition in accordance with the RevAssist® program.

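### The only patient diary prints lenalidomide on every day from 1 to 21, although one of the protocol's lenalidomide reduction steps is taken every 48 hours

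*Combined protocol and SAP*

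**What the plan says.** **The diary.** Section 5.7.6 names Appendix VII as the form on which subjects record drug administration, and no other diary appears in the documents. It tells the patient that "Revlimid® (lenalidomide) should be taken from day 1-21", prints R in every cell from day 1 to day 21, and adds "Please call your study nurse when you take the 21st dose of Revlimid". The day 21 cell also carries a call mark. Days on which a drug was not taken are left blank, "irrespective of the reason, whether you were advised by your physician or simply forgot". There is no field for the dose, no alternate-day version, and no limit on the cycles in which the weekly D for dexamethasone is printed.

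**The lenalidomide regimens.** For patients with GFR 30-59 ml/min the synopsis states "Lenalidomide will be used at a fixed dose of 10mg daily from day 1-21 every 28 days". In Section 5.7.1.1, Table 2 takes 10 mg daily down to "15 mg every 48 hours during Days 1-21 every 28 days". Section 5.7.3 confirms the ranking: the first increase from the every-48-hour step is to 10 mg daily. Footnote 3 in Section 5.6.2.3 says of a dose: "If it is missed for the entire day, it should not be made up".

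**Dexamethasone.** Section 5.6.2.4 states "After six 28-day cycles on combination therapy, dexamethasone and azacitidine will be discontinued", with continuation or restart at physician discretion in defined cases.

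**The concern.** Lenalidomide is self-administered, and the diary is the written sheet the patient keeps at home. The every-48-hour step raises the single dose from 10 mg to 15 mg. It is a reduction only because of the longer interval, and the interval is exactly what the printed grid does not show. If the grid is read as the schedule, the patient takes more per day than before the reduction. Patients on this step have, or have had, impaired renal clearance.

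The record is affected even when nobody makes a mistake. On this step 10 of the 21 printed R cells are correctly left blank, and a blank for a day that was never assigned looks the same as a blank for a missed dose. Section 5.7.6 has staff reconcile drug counts with this sheet.

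**Working it through.** The documents give no cycle-total dose, so there is no stated figure to reproduce. The check is dose arithmetic plus a reading of which patients reach the step.

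**1. Number of doses in days 1-21**
- Diary grid: 21.
- Every 48 hours from day 1: days 1, 3, ..., 21 = 11 (10 if started on day 2).
- Days on which grid and step disagree: 21 - 11 = 10.

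**2. Lenalidomide per cycle (mg per dose x doses)**

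| Regimen | Calculation | Total | Against 10 mg daily |
|---|---|---|---|
| Before reduction | 10 x 21 | 210 mg | reference |
| Table 2 step as written | 15 x 11 | 165 mg | 165/210 - 1 = -21% |
| Same, started on day 2 | 15 x 10 | 150 mg | 150/210 - 1 = -29% |
| 15 mg on every printed R, 21 capsules available | 15 x 21 | 315 mg | 315/210 - 1 = +50% |

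Against the Table 2 step, 315/165 - 1 = +91%.

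**3. Effect of the supply limit.** Sections 5.1.1.6 and 5.1.1.8 limit supply to one cycle. Assume one 15 mg capsule per dose and exactly 11 dispensed. A patient following the grid then uses all 11 by day 11, and the cycle total remains 165 mg. Through day 11:
- grid followed: 15 x 11 = 165 mg
- previous 10 mg daily: 10 x 11 = 110 mg, so 165/110 - 1 = +50%
- every 48 hours as written (days 1, 3, ..., 11 = 6 doses): 15 x 6 = 90 mg

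No drug is left for days 12-21.

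**4. Who reaches the step**
- *Renal route, clear.* When clearance falls below 30 ml/min, Table 5 holds the drug and then restarts it at the next lower level, citing Table 2. From 10 mg daily that level is the every-48-hour step. Patients in the GFR 30-59 cohort start at 10 mg daily. A patient enrolled at 25 mg first goes to 10 mg daily and meets this step second.
- *Other toxicities, unclear.* Table 1 excludes toxicities in the presence of renal impairment. Table 2's title covers other toxicities only after a dose reduction for renal impairment. A patient who started at 10 mg without a prior reduction is excluded by the first title and not plainly included by the second. This matters because, for neutropenia or thrombocytopenia on combination therapy, Table 5 reduces lenalidomide in patients whose myeloma has been refractory to it.
- *Timing.* Table 5 allows a restart at a reduced level before day 21, when the patient may already hold a sheet with the daily grid.

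**5. The call wording.** With 11 doses in days 1-21, a 21st dose does not occur in the cycle. A daily patient who misses one dose reaches at most 20, because missed doses are not made up. In both cases the sentence and the day 21 call mark disagree.

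**The case against.** The strongest reply is that the diary is a record form, not a prescription. Section 5.7.6 has staff review dosing instructions with subjects, the sheet allows blanks on physician advice, supply is limited to one cycle, and used and unused drug is counted and reconciled with the diary. The diary sentence about days 1-21 does not itself say daily, and Table 2's step also runs within days 1-21. The conflict therefore lies in the 21 printed Rs and the reference to a 21st dose. All of this is correct. It makes the error less likely and easier to detect, but none of it corrects the sheet.

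A reader might draw four stronger conclusions that the documents do not support:
- *That the diary turns the reduction into a 315 mg cycle.* This needs 21 capsules of 15 mg, which the one-cycle supply rule is meant to prevent, and a patient who follows the grid over individual instructions. It is an upper bound, and the documents give no basis for its frequency.
- *That a correct every-48-hour patient is scored 52% adherent (11/21) and a wrongly daily patient looks perfect.* No doses-over-21 measure is defined in Section 5.7.6 or Section 10, and 21 crossed cells could not be reconciled with 11 capsules.
- *That this is the first lenalidomide reduction for every GFR 30-59 patient.* The two table titles leave that open for non-renal toxicities. The maximum of 12 additional patients under amendment 7 is an enrolment ceiling, not a count of patients who reach this step.
- *That resupply or dexamethasone control rests on this sheet.* The day 21 call mark exists, schedule footnote 10 suggests prescribing 5 to 7 days ahead, and footnote 12 limits dexamethasone to cycles 1 to 6 with a prescription check each cycle. These remain drafting inconsistencies.

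**Conclusion.** The inconsistency is real. The only diary shows a daily lenalidomide grid that contradicts a reduction step in Table 2, and a patient on that step who followed it would take 15 mg/day where 10 mg/day had been taken before. On the assumption of one 15 mg capsule per dose and 11 dispensed, the consequence is 165 mg taken in about 11 days, 50% above the previous daily rate, followed by no drug. Without that supply limit the ceiling is 315 mg. How many patients reach the step, and how many would follow the grid, cannot be derived from the documents. Separately, and without any patient error, a blank cannot distinguish a day not assigned from a missed dose.

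Two smaller inconsistencies belong with it: D is printed without a cycle limit although Section 5.6.2.4 stops dexamethasone after six cycles unless continued, and the 21st-dose wording departs from the day 21 call mark after any missed dose.

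This is a low-cost safety correction rather than an essential one. The primary endpoint is DLT in cycle 1, the starting lenalidomide regimen in both cohorts matches the grid, and no planned analysis uses the diary. No position is taken on which lenalidomide regimen should apply.

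**What to change.** Reconcile Appendix VII with Tables 1 and 2 and with Sections 5.6.2.4 and 5.7.6:

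1. Issue the diary per patient and cycle from the assigned regimen, with the assigned dose shown and R and D printed only on assigned days. Reissue it at any mid-cycle change.
2. Drop the 21st-dose sentence and keep only the day 21 call mark.
3. State in Section 5.7.6 that diary and drug counts are reconciled against the doses assigned for that cycle.
4. Align the titles of Tables 1 and 2 so that it is clear which table governs non-renal toxicities in patients who start at 10 mg daily. Which one applies is for the protocol team to decide.

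The cost is an additional diary template, one sentence in Section 5.7.6 and an edit to two table titles. No patients, visits or procedures are added.

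### The patient diary gives two different sets of dexamethasone days, and the set in its instruction sentence falls on azacitidine days, which breaks the protocol's own 24-hour separation rule

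*Combined protocol and SAP*

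**What the plan says.** Appendix VII is the diary that patients keep for lenalidomide and dexamethasone. Its instruction sentence says that lenalidomide "should be taken from day 1-21 and dexamethasone on day 1, 8, 15, and 22". The grid below marks D on days 2, 9, 16 and 23. Days 1, 8 and 15 carry only an R (lenalidomide), and day 22 is empty. Patients are asked to "cross out the D if you took dexamethasone on the indicated days", and then: "Please leave blank if you did not take the indicated drugs on the respective day".

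Section 5.6.2.3 sets the dosing. Two columns of its table are headed "Azacitidine (s.c.)* Starting day 1" and "Lenalidomide (p.o.) Starting day 1". The dexamethasone column has no start day and gives only a once-weekly frequency. Footnote 2, for twice-weekly dosing, says: "Azacitidine should be administered on the same days each week, +/- one day is allowed", and adds: "The following schedules are recommended: Monday-Thursday, Monday-Friday, Tuesday-Friday, Tuesday-Saturday". Footnote 1 keeps weekly azacitidine (dose levels 1 and 2) ideally on one fixed weekday, with up to two days' leeway. Footnote 4 places dexamethasone at breakfast and states: "Dexamethasone should be taken at least 24h after and not less than 24h before azacitidine to maximize the s-phase specific epigenetic effects of azacitidine".

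**The concern.** The diary is the only place in the protocol that names calendar days for dexamethasone, and it names two incompatible sets. The set in the sentence appears to coincide with azacitidine, which is the overlap footnote 4 is written to prevent.

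Two things are at stake. First, dexamethasone is taken at home on this instruction. Followed as written, the sentence breaks the separation rule in every combination cycle. That includes cycle 1, the interval between the two research marrow samples (section 5.5.2) that feed the secondary demethylation and gene-expression endpoints. Secondly, the diary is a compliance record that staff reconcile with drug counts (section 5.7.6). A patient who follows the sentence must either leave the D blank, which the diary defines as not taken, or cross it out on a day when no dose was taken.

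**Working it through.** No sample-size or error-rate figure is involved. The check compares calendars and then hours.

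**Inputs**
- Sentence days (Appendix VII): 1, 8, 15, 22.
- Grid days (Appendix VII): 2, 9, 16, 23. The same one-day offset appears in all four weekly rows, so a broken table does not explain it.
- Azacitidine (section 5.6.2.3): first dose on day 1, then the same weekday or weekdays each week.
- Recommended pairs: Monday–Thursday, Monday–Friday, Tuesday–Friday and Tuesday–Saturday. Each can begin on either day of the pair, giving 4 × 2 = 8 calendars. In all 8 the second injection comes 3 or 4 days after day 1.
- Combination treatment: six cycles (section 5.6.2).

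**Step 1: sentence against grid.** The sets {1, 8, 15, 22} and {2, 9, 16, 23} have no element in common. D boxes on sentence days: 0 of 4.

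**Step 2: each set against the nominal azacitidine days.**

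| Azacitidine schedule | Azacitidine days | Sentence doses on an azacitidine day | Grid doses on an azacitidine day | Grid dose: days since last / to next injection |
|---|---|---|---|---|
| Weekly | 1, 8, 15, 22 | 4 of 4 | 0 of 4 | 1 / 6 |
| Twice weekly, 3-day gap | 1, 4, 8, 11, 15, 18, 22, 25 | 4 of 4 | 0 of 4 | 1 / 2 |
| Twice weekly, 4-day gap | 1, 5, 8, 12, 15, 19, 22, 26 | 4 of 4 | 0 of 4 | 1 / 3 |

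Over six cycles this is 6 × 4 = 24 of 24 for the sentence and 6 × 0 = 0 of 24 for the grid.

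**Step 3: the rule in hours.** Let d be the clock time of dexamethasone (breakfast) and a the clock time of the injection.
- Sentence day: the gap is |d − a|, always less than 24 h. The rule fails at any clock time.
- Grid day, after the injection: the gap is 24 + (d − a) h. This meets the rule when a is no later than d, and falls short when the injection is later than breakfast.
- Grid day, before the next injection (tightest case, 2 calendar days): the gap is 48 + (a − d) h, always more than 24 h.

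The grid can therefore miss the rule on one side only, when injections are given after the breakfast hour. The documents give no injection time, so the range for the grid in hours is 0 to 24 of 24 doses.

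**Step 4: permitted shifts.** Moving the first injection of a week by +1 day (for example day 8 to day 9) puts that week's grid dose on an azacitidine day, 1 of 4. A fixed printed day is therefore not enough without a line restating the rule.

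**The case against.** The strongest opposing case accepts the contradiction and disputes its weight.

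- **The rule is in hours, and the calendar count flatters the grid.** This stands as a limit. With breakfast dosing and clinic injections later in the day, a day-2 dose is under 24 h after the injection. The grid is the version consistent with footnote 4 by calendar day, but it does not guarantee 24 h. If injections usually follow breakfast, the exception in the proposed added line would be used often. Day 3 would then fit better: the gaps would be 48 + (d − a) h after the day-1 injection and 24 + (a − d) h before a day-4 injection, both at least 24 h when a is no earlier than d. None of this helps the sentence, which fails at every clock time.
- **24 of 24 is 4 of 4 multiplied by six.** True. It assumes that a patient follows the sentence rather than the D boxes in every cycle, uncorrected. The per-cycle figure is the basic one.
- **Safeguards exist.** Staff review the dosing instructions with patients and reconcile the diary (section 5.7.6), and footnote 4 is available to them. The number of doses per cycle stays at four, so the tablet count itself is sound and only the diary entry or its date is wrong. This lowers the likely harm but leaves a wrong instruction in the patient's hands.
- **The consequence is not quantified.** Footnote 4 is worded as a recommendation, and section 10 contains no analysis that uses the dexamethasone day. This stands, and it limits how serious the point is.

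**Conclusion.** The concern holds. The diary contradicts itself, and the sentence is the version in error, because it cannot satisfy footnote 4 under the weekly schedule or any recommended twice-weekly pair. The counts in step 2 rest on the nominal calendar; azacitidine may move by one day (twice weekly) or two days (weekly), which can change individual weeks.

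The documents do not show which version patients followed, or how much overlap would alter demethylation or gene expression. The primary endpoint, dose levels and sample size do not depend on it. The point should be corrected because patients act on this page, but it does not threaten the trial's main conclusion.

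**What to change.** 1. Change the diary sentence so that dexamethasone is on days 2, 9, 16 and 23, matching the grid.
2. Add one line for patients: leave at least 24 hours after the last azacitidine injection and at least 24 hours before the next, and agree another day with study staff if an injection is moved or was given later in the day than the usual dexamethasone time.
3. Optionally, add a field for the actual date and time of each dexamethasone dose.

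If the sites know that injections are routinely given after breakfast, they should settle the default day with that in mind and print the same day in both the sentence and the grid.

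The cost is one reissued diary page. Nothing changes in the design, endpoints or sample size.
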